Clinical Trial Protocol

**Title : Immediate versus Deferred
Cytoreductive Nephrectomy with
Ipilimumab/Nivolumab in Metastatic
Clear Cell Renal Cell Carcinoma: A
Multicenter, Randomized, Open-Label
Phase III Trial**

Principal Investigator:

**[name], PhD
(Seoul National University Hospital)**

Document date : 12th, August, 2025

Study Objectives

The primary objective of this trial is to establish the optimal treatment strategy for patients with synchronous metastatic clear cell renal cell carcinoma (mRCC) in the era of immune checkpoint inhibitors by comparing upfront versus deferred cytoreductive nephrectomy (CN) combined with ipilimumab and nivolumab.

Study Design

This is a multicenter, randomized, open-label, phase III clinical trial conducted at 12 sites in Korea. A total of 172 participants with IMDC intermediate- or poor-risk mRCC will be randomized 1:1 to either upfront CN followed by ipilimumab/nivolumab induction and nivolumab maintenance, or ipilimumab/nivolumab induction followed by deferred CN and nivolumab maintenance. Participants will be followed for 15 months.

Arms and Interventions

Arm A (Experimental): Upfront CN → 4 cycles ipilimumab/nivolumab → nivolumab maintenance

Arm B (Experimental): 4 cycles ipilimumab/nivolumab → Deferred CN → nivolumab maintenance

Primary Outcome Measure

Progression-Free Survival (PFS): Time from randomization to first documented disease progression or death from any cause, assessed up to 15 months.

Secondary Outcome Measures

- Overall Survival (OS)
- Surgical morbidity (Clavien-Dindo classification, CTCAE v4.0)
- Radiologic tumor response (RECIST v1.1)
- Rate of unresectable tumors in deferred CN arm
- Effect of CN on early progression (within 4 weeks post-surgery)
- Comparison of surgical approach and extent
- Quality of life (QoL) assessments

Eligibility Criteria

Inclusion: Adults ≥ 19 years, histologically confirmed synchronous clear cell mRCC, IMDC intermediate- or poor-risk, ECOG 0–1, measurable metastatic lesion, resectable primary tumor, life expectancy >3 months, informed consent.

Exclusion: Prior systemic therapy for mRCC, other malignancy within 2 years, significant uncontrolled comorbidities, autoimmune disease, chronic immunosuppressive therapy, or deemed unsuitable by investigator.

Sample Size

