A total of 172 participants (86 per arm) are required to detect a difference in PFS between arms, assuming 15-month PFS of 72% in upfront CN vs 87% in deferred CN, with 80% power and a two-sided alpha of 0.05.

Safety Assessments

Safety will be monitored through perioperative complication rates and immune-related adverse events (irAEs) associated with ipilimumab/nivolumab. Monitoring will follow CTCAE v5.0 and Clavien-Dindo classification.

Study Methods

1. Institutional Review Board (IRB) approval will be obtained from all participating institutions. The coordinating institution (Seoul National University Hospital) will establish a Data Management Plan and Data Quality Control plan, and will implement a randomization system and electronic case report form (eCRF) system. Randomization schedules will be generated by the Medical Research Collaborating Center (MRCC) using a web-based permuted block randomization approach. The coordinating institution will conduct data monitoring and external audits through its Clinical Trials Center.
2. **Enrollment:** Eligible patients with metastatic renal cell carcinoma (intermediate or poor risk) will be identified during outpatient visits. The investigator or sub-investigator will provide sufficient explanation and obtain written informed consent.
3. A biopsy of the renal mass will be performed to confirm clear cell RCC.

4. **Pre-treatment evaluations and procedures:** Baseline tests and perioperative care will be performed identically in both Arm A (Deferred CN) and Arm B (Upfront CN).
5. **Randomization:** Randomization will be performed immediately after screening using permuted block randomization, stratified by IMDC intermediate vs poor risk group. This study is conducted in an open-label design.
6. **Interventions:** Participants will follow the treatment schedule according to their randomized group.

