 - **Upfront CN Arm:** Patients will undergo upfront cytoreductive nephrectomy. Peripheral blood mononuclear cells (PBMCs) will be collected preoperatively, postoperatively, and after completion of 4 cycles of ipilimumab/nivolumab. Four weeks after surgery, perioperative complications and progression status will be evaluated. Based on these findings, patients will receive 4 cycles of ipilimumab/nivolumab induction within 6 weeks after surgery, followed by assessment of progression status, safety, and quality of life (QoL). Thereafter, maintenance nivolumab will be administered with assessments every 3 months. At 15 months after treatment initiation, progression and survival status will be determined.
 - **Deferred CN Arm:** Patients will receive 4 cycles of ipilimumab/nivolumab induction therapy. PBMCs will be collected before and after induction. Following induction, progression status, safety, and QoL will be assessed, after which deferred cytoreductive nephrectomy will be performed. Additional PBMCs will be collected after surgery. Four weeks postoperatively, perioperative complications and progression status will be evaluated. Thereafter, nivolumab maintenance will be given with assessments every 3 months. At 15 months after treatment initiation, progression and survival status will be determined.

Additional Considerations:

- If progressive disease (PD) is observed during induction therapy, this will be defined as the progression event for the primary endpoint. At the investigator's discretion, patients may switch to second-line systemic therapy or undergo CN.
- For patients with response or stable disease (complete response, partial response, or stable disease), CN will be planned after induction therapy (approximately 3 months). However, considering potential clinical or logistical delays, a window period of up to 3.5 months after completion of induction will be allowed for surgery. During this window, additional nivolumab maintenance therapy may be administered.

9. **Perioperative management and documentation:** Pre- and post-surgical management and documentation will be standardized across both study arms.

10. Follow-up: Participants will be followed for 15 months from treatment initiation. Data will be collected at each immunotherapy cycle and during follow-up visits, with additional perioperative outcomes collected for 3 months post-surgery.

Data and Safety Monitoring

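### The safety scope has no place for primary-tumour complications before deferred nephrectomy, so harms are captured unequally between the arms

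*Protocol*

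**What the plan says.** The Safety Assessments section sets the scope: "Safety will be monitored through perioperative complication rates and immune-related adverse events (irAEs) associated with ipilimumab/nivolumab". The sentence after it reads "Monitoring will follow CTCAE v5.0 and Clavien-Dindo classification". That sentence chooses grading scales and adds no further kind of event.

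Among the Secondary Outcome Measures, the only safety-type item is "Surgical morbidity (Clavien-Dindo classification, CTCAE v4.0". One consequence of waiting is listed separately: "Rate of unresectable tumors in deferred CN arm". PFS, OS and QoL are also outcomes.

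On timing, the Additional Considerations under Study Methods plan deferred CN after induction, with about 3 months given in brackets, and add that "a window period of up to 3.5 months after completion of induction will be allowed for surgery". After progression during induction, CN is at the investigator's discretion, so some deferred-arm patients may never have it.

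On collection, the Follow-up item of Study Methods says: "Data will be collected at each immunotherapy cycle and during follow-up visits, with additional perioperative outcomes collected for 3 months post-surgery". The description of the deferred arm also schedules a safety assessment once induction ends, before surgery. Neither place says what is to be recorded.

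**The concern.** The trial asks when the primary tumour should be removed. Early removal brings surgical harm forward. Later removal leaves the tumour in place, with whatever it may cause in the meantime. A fair account of the two strategies has to record both kinds of harm on the same basis.

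The stated scope covers the first kind and treatment-related immune harm, but not the second. Suppose a deferred-arm patient is admitted in month 2 with bleeding from the kidney tumour. There has been no operation and the event is not immune-related, so nothing in the protocol requires it to be recorded as a safety event. An upfront patient who bleeds after nephrectomy is recorded.

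The trial is meant to inform treatment guidelines, so a reader of its results will weigh harms alongside PFS. Events that were not recorded prospectively may not be recoverable later, and a statistical analysis plan cannot analyse data that were never collected. That is why the protocol wording matters here.

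**Working it through.** The protocol states no figure for this kind of harm, so there is none to reproduce. The check compares the sections and then works out the length of the exposure.

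**Step 1. Where could such an event be recorded?** Take a non-fatal complication of the primary tumour, not counted as progression, before deferred CN.

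| Place in the protocol | Does it require the event to be recorded? |
|---|---|
| Perioperative complications (Safety Assessments) | No: there has been no operation |
| irAEs (Safety Assessments) | No: not immune-related |
| Surgical morbidity (secondary outcome) | No: there has been no operation |
| Perioperative collection for 3 months (Follow-up) | No: it starts with surgery |
| PFS, OS | No: neither progression nor death |
| Unresectability in the deferred arm | Only if the tumour becomes unresectable |
| QoL | Perhaps indirectly, as a lower score, not as an event |
| Safety assessment after induction; data at each cycle and visit | Possible, but content not stated |

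Only the last row could capture the event as such, and the only description of safety that the protocol offers is the two-category one.

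**Step 2. How long is the exposure?** If the bracketed 3 months is the length of induction:

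- shortest planned time with the primary in place: about 3 months;
- longest permitted: 3 + 3.5 = 6.5 months;
- without CN: the rest of follow-up, up to 15 months from treatment initiation.

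If instead the 3 months is the gap between induction and surgery, the total cannot be computed, because the length of induction in months is not given elsewhere. It would then exceed 3 months. The interval from randomization to first treatment is not stated either and would be added in both arms.

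**Step 3. Exposure in 86 deferred-arm patients**, on the first reading and if all have CN:

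- 86 × 3 = 258 person-months;
- 86 × 6.5 = 559 person-months, if every patient used the whole window.

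These figures measure exposure, not bias. They leave out the longer exposure of patients who never have CN.

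**Step 4. How many events?** The protocol gives no rate. For assumed proportions of deferred-arm patients with an event in neither category:

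| Assumed proportion | 86 × proportion | Patients |
|---|---|---|
| 2% | 1.72 | about 2 |
| 5% | 4.3 | about 4 |
| 10% | 8.6 | about 9 |
| 15% | 12.9 | about 13 |

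The range is illustrative, and it supposes that none of these events is recorded at any visit.

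**The case against.** The strongest reply is that the scope sentence does not say only. It names two things through which safety is monitored and does not forbid others. Data are collected at each cycle, and safety is assessed after induction, so the waiting period does have contacts at which an event could be noted. The electronic case report form and the Data Management Plan are mentioned but not shown, and may be broader. What stands is that capture is possible. It is not required, and no section gives those contacts a content wider than the two categories.

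A second reply is that part of the harm of waiting is already measured. This is correct. Progression during induction is a primary-endpoint event, deaths enter PFS and OS, unresectability is a named outcome, and QoL is assessed. It narrows the gap to non-fatal complications that are not progression, but does not close it.

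Third, the gaps do not all run one way. Deferred-arm patients who have CN contribute perioperative complications too. Both arms receive the same drugs and have irAEs counted. An upfront patient who never starts immunotherapy contributes no irAEs, and other events that are neither surgical nor immune-related may be lost in either arm. The direction is therefore likely, not certain.

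A reader might also go further and infer three things that the protocol does not support:

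- That the safety comparison is biased towards deferral by definition. No overall between-arm safety comparison is defined beyond surgical morbidity.
- That the monitoring committee would be blind to this risk. The protocol does not say what the committee receives.
- That open-label attribution of irAEs adds to the imbalance. Both arms get the same drugs, no directional incentive is shown, and this is separate from harm by the retained tumour.

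**Conclusion.** The point holds in a limited form. As written, the safety scope gives no category to non-fatal complications of the primary tumour, other than progression, between randomization and deferred CN or in patients who never have CN. Such events can arise almost only in the deferred arm, provided that the wait for upfront surgery, which the protocol does not state, is short. Capture is therefore unequal, probably in the deferred arm's favour.

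The exposure is about 3 to 6.5 months per patient if the bracketed 3 months is the length of induction, and longer without CN. The size of the imbalance cannot be derived. The counts of about 2 to 13 of 86 follow from assumed rates of 2% to 15% and are not estimates. How often a retained primary causes such events is clinical background that the protocol does not give. The conclusion rests on the lack of any stated requirement for all-cause recording, not on evidence that events would in fact be missed.

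**What to change.** Reword Safety Assessments so that all adverse events of any cause, graded by CTCAE, are recorded from randomization to the end of follow-up in both arms, at the cycles and visits already planned. Summarise them by arm per randomized participant, so that patients who never have CN or never start immunotherapy stay in the denominator. Keep perioperative complications and irAEs as labelled subsets and add primary-tumour complications as a third. State in the Follow-up item that this is what the per-cycle and visit data include. Name one CTCAE version while doing so, since the outcome list cites v4.0 and Safety Assessments cites v5.0.

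The cost is a change of protocol wording, a broader adverse-event form and more events for sites to enter. No visit is added, and no treatment or clinical rule changes.

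### Could the swapped Arm A and Arm B labels in the protocol reverse the allocation or the treatment effect?

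*Protocol*

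**What the plan says.** Under Arms and Interventions the protocol gives "Arm A (Experimental): Upfront CN → 4 cycles ipilimumab/nivolumab → nivolumab maintenance" and "Arm B (Experimental): 4 cycles ipilimumab/nivolumab → Deferred CN → nivolumab maintenance". Arm A is therefore surgery first, and Arm B is induction first.

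Study Methods item 4 (pre-treatment evaluations) states: "Baseline tests and perioperative care will be performed identically in both Arm A (Deferred CN) and Arm B (Upfront CN". Here the letters are the other way round. Both statements are in the current text, and neither is said to take precedence.

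The rest of the protocol uses no letters. Study Design says that participants "will be randomized 1:1 to either upfront CN followed by ipilimumab/nivolumab induction" or to the induction-first sequence. The treatment schedules under Study Methods item 6 open with "Upfront CN Arm: Patients will undergo upfront cytoreductive nephrectomy" and "Deferred CN Arm: Patients will receive 4 cycles of ipilimumab/nivolumab induction therapy". The sample-size assumption and the secondary outcome on unresectable tumors also refer to upfront or deferred surgery by name.

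**The concern.** Two opposite definitions of one label cannot both be right. The slip sits just before the randomization step in the Study Methods, which sites will read closely. Both arms are called experimental, so there is no control label to show which is which.

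If a programmer built the allocation list from one section and a site or analyst worked from the other, two things could go wrong. Participants could receive the sequence opposite to their allocation, or the sign of the treatment effect could be inverted at analysis. The trial's one primary question is which sequence gives longer progression-free survival, so an inversion would reverse its answer.

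**Working it through.** **Step 1. Where the letters are used.**

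| Place in the protocol | How the arms are named |
|---|---|
| Study Design | By strategy |
| Arms and Interventions | A = upfront, B = deferred, strategy written out |
| Secondary outcomes (unresectable tumors) | By strategy (deferred) |
| Sample Size | By strategy (72% upfront, 87% deferred) |
| Study Methods item 4 | A = deferred, B = upfront, strategy written out |
| Study Methods item 6, both schedules | By strategy |

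The letters appear in two rows only and never stand without the strategy beside them. Item 4 states that baseline work-up and perioperative care do not differ between the arms. A statement of sameness reads the same with the labels exchanged.

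**Step 2. Does any planned figure depend on the letters?** The inputs are from Sample Size: 72% and 87% at 15 months, 80% power, two-sided alpha 0.05, 86 per arm. The pooled two-proportion formula, with mean rate 0.795, is

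n = [1.96 × √(2 × 0.795 × 0.205) + 0.842 × √(0.72 × 0.28 + 0.87 × 0.13)]² / 0.15² ≈ 113 per arm.

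This does not reproduce the stated 86 per arm. That is a separate matter, which the lettering neither causes nor cures. For the present point, the formula is symmetric in the two rates:

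| Quantity | Rates as stated | Rates exchanged |
|---|---|---|
| Pooled n per arm | 113 | 113 |
| Power at 86 per arm | 68.6% | 68.6% |
| Events (Schoenfeld) | 43 | 43 |
| Events (Freedman) | 48 | 48 |

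**Step 3. What would a real swap do?** The protocol states no hazard ratio. Assuming proportional hazards, the two rates imply ln(0.87)/ln(0.72) = 0.424 for deferred against upfront, and a full inversion gives 1/0.424 = 2.36.

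If a share m of each arm received the other sequence, the difference would be

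[(1 − m) × 87 + m × 72] − [(1 − m) × 72 + m × 87] = 15 × (1 − 2m) points,

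which is 12 points at m = 10% and 9 points at m = 20%. Both values of m are assumptions with no basis in the document. These results show what mislabelling would do in any two-arm trial with these rates. They do not make it likely here.

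**Step 4. Is there a documented route to a swap?** Study Methods item 1 says who generates the schedules and that the coordinating institution sets up the randomization and data-capture systems. It does not say how the arms are coded. Item 6 sends each participant to the schedule of the randomized group, and those schedules carry strategy names.

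**The case for a change.** The best case for acting is that the contradiction is certain, not a matter of reading. It is in the current text, and nothing in the document breaks the tie. The protocol is the source from which the randomization system, the data-capture form and the analysis programs are built, and a later analysis plan cannot make both definitions true. Two careful readers could code the arms oppositely, and each could cite the protocol. Open-label conduct helps to expose a wrong treatment at the bedside but protects less against an inverted code in a dataset. The correction costs one line.

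The inconsistency itself stands, and so does the point that a coding error in a dataset is harder to see than a wrong operation. The step from there to harm is not supported. It needs a list or form keyed by bare letters, and the protocol describes none. It also needs the inversion to go unnoticed although the arms differ in whether nephrectomy comes before or after four induction cycles. Data are recorded at each immunotherapy cycle and perioperative outcomes are collected, so the order of treatment should be visible in the database. Monitoring, external audit and a data quality control plan are also provided for.

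**Conclusion.** The labels do conflict, but this is a clerical slip and calls for no change to the plan. Anyone following the protocol as written gives the same two treatment sequences, compares the same two groups and reaches the same conclusion under either lettering. The effect on sample size, power and required events is zero. The swing in the hazard ratio from 0.42 to 2.36 and the dilution to 12 or 9 points are hypothetical. They rest on proportional hazards, on assumed shares of swapped participants and on letter-keyed coding that the document does not show.

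The conclusion assumes that the systems and the analysis identify the arms by strategy, as the operative text does, or by one consistent code. Matching the two sections at the next edit, with a glance at the system coding, is ordinary housekeeping.
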